Our optimized DWI pulse sequence includes a combination of new improvements in data acquisition—, specifically multiband echo planar imaging (MultiBand, Siemens Medical Solutions, Erlangen, Germany) and multi-segment K-space readout algorithm (RESOLVE, Siemens Medical Solutions, Erlangen, Germany), i.e. SMS/RESOLVE WIP 1051a. The multiplexed sensitivity encoding algorithm (the MUSE method pioneered by [name] of the University of Arizona, Figure 1) is applied at post processing. Our optimized DWI sequence follows QIBA-recommended guidelines. We found that our DWI pulse sequence improved quantitative artifact parameters [[name], 2019] which in turn should increase the diagnostic accuracy of our technique.

We plan to enroll 60 biopsy-proven neck SCC patients after treatment with surgery, radiation or chemo-radiation. The Otolaryngology, Head and Neck Surgery physicians and their clinic staff will coordinate enrollment. The patients will undergo an optimized research neck DWI protocol up to 3 weeks post-treatment and then a standard-of-care 3-6 months post-treatment FDG PET/CT examination. The optimized research DWI images will be acquired on a dedicated research Siemens 3T Scanner belonging to Washington University's Center for Clinical Imaging Research. The standard-of-care FDG PET/CT will be acquired at one of the Siemens Biograph clinical **PET/CT units located throughout the Barnes-Jewish Hospital Systems that adhere to QIBA FDG PET/CT protocols**. We will compare the ADC values (ADCmin and ADCmean) from the optimized DWI pulse sequence to FDG PET SUVmax. We will follow patients for 1 year to assess their clinical outcomes, including histological results associated with re-biopsy or surgery.

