## 3.0 PARTICIPANT SELECTION

### ELIGIBILITY CRITERIA

#### Inclusion Criteria:

- 1) Histologically-proven newly diagnosis or recurrence as indicated by tissue diagnosis of T3 or T4 squamous cell carcinoma of the head and neck
- 2) Must have had or be scheduled for standard-of-care surgical resection, radiation, and/or chemo-radiation of the diagnosed squamous cell carcinoma of the head and neck
- 3) At least 18 years of age
- 4) Patient must be able to understand and willing to sign a written informed consent document.

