## **4.0 STUDY PROCEDURES**

### **IMAGING PLAN**

Overview: 60 biopsy-proven neck SCC patients after treatment with surgery, radiation or chemo-radiation will be enrolled for this trial. The Otolaryngology, Head and Neck Surgery physicians and their clinic staff will assist in coordinating enrollment. The patients will undergo an optimized research neck DWI MRI, up to 3 weeks post-treatment and then a standard-of-care 3-6 months post-treatment FDG PET/CT examination. (\*\*Note: Patients who do not undergo SOC PET/CT at the 3-6 month time point will be considered inevaluable and will be replaced.) Patients who sign the consent form but do not have the MRI will not be considered accrued on this study. The optimized DWI images will be acquired on a dedicated research Siemens 3T Scanner belonging to Washington University's Center for Clinical Imaging Research. The standard-of-care FDG PET/CT mages will be acquired at one of the Siemens Biograph clinical PET/CT units located throughout the Barnes-Jewish Hospital Systems. We will compare the ADC values (ADCmin and ADCmean) to the optimized DWI sequence to FDG PET

SUVmax. For up to 1 year post-treatment, patients' medical records will be reviewed after scheduled SOC visits to additionally assess for clinical outcomes.

	Baseline	up to 3 Weeks Post-Treatment	3-6 Months Post-Treatment	Follow up for up to 1 year post-treatment
Screening	X			
Enrollment	X			
Medical Record Review	X	X	X	X
DWI MRI		X		
FDG PET/CT			SOC	

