### Clinical Data to be Collected

**The following clinical data points will be collected and recorded in REDCAP (Please see attached data sheet):**

- Age
- Birth Gender
- Original Cancer Stage
- Date of original diagnosis
- Cancer Location
- Cancer Stage
- HPV Status
- Cancer Treatment (choice=Surgery)
- Cancer Treatment (choice=Chemotherapy)
- Cancer Treatment (choice=Radiation)
- Surgery Date
- Radiation Dosage
- Chemotherapy Type/Dosage
- Chemotherapy treatment range
- Date of Completion of Initial Treatment
- Smoking Pack Year History
- Date of Study MRI
- Why enrolled?
- MRI Imaging uploaded
- Biopsy Obtained
- Pathology confirms recurrence
- Date of recurrence diagnosis
- Length of time from MRI to clinical/radiographic progression
- Last clinical F/U
- Last imaging F/U
- Treatment after repeat biopsy/surgery

**Duration of Imaging:** MRI data to include anatomical MPRAGE volumetric T1, fat-saturated T2-weighted image (for anatomical localization and cystic/necrotic changes) and optimized research DWI sequence will be acquired in 30 minutes. If at any time the constraints of this protocol are considered detrimental to the patient's health and/or the patient no longer wishes to continue

imaging, the protocol should be discontinued and the reason(s) for discontinuation documented in the case report forms.

**Post-imaging:** While there are no anticipated problems during the research imaging, continuous monitoring for any adverse events or abnormal events will occur during imaging. Once the research MRI is complete, the subject will be asked by a member of the study team how they are feeling prior to leaving the CCIR. If for any reason, the subject is feeling abnormal, [name] or [name], the on-site neuroradiologist, will be notified and will address any adverse events.

**Patient Compensation:** Subject will receive \$100 at the completion of their research DWI MRI imaging. Subjects will be provided compensation by check.

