## **MRI PROCESSING GUIDELINES**

**Overview:** All MRI studies will be blindly evaluated by at least two experienced neuroradiologists (Drs. [name] and [name]). If there is an urgent or emergent finding obtained by the research MRI study, this will be communicated by one of the neuroradiologists directly to the ENT physician for follow up who is caring for the patient, as per normal departmental protocol. In the case of this study, incidental findings are defined as anything not already noted in the medical record.

**Methodology of MRI Evaluation:** The research MRI study of the head and neck will be performed on a Siemens 3T MRI Scanner system located in the Center for Clinical Imaging Research (CCIR). Multiplanar / multisequence MRI data including the optimized research DWI sequence will be acquired. MRI subjects must complete an MRI screening evaluation form before entering MRI zone 3 or the scanning room. Images will be anonymized and sent to CNDA for archiving after diagnostic reports are complete. All anonymized MRI studies will then be blindly evaluated by at least two experienced neuroradiologists (Drs. [name] and [name]). MUSE image processing will be applied post-acquisition.

**Methodology of ADC Evaluation:** The primary tumor, suspicious lesion, and/or area of post-treatment change will be first identified in the anatomical images and then outlined in the ADC sequence by experienced neuroradiologists (Drs. [name] and [name]), excluding areas of cystic change and necrosis. If there are multiple lesions, only the dominant lesion with the lowest ADC will be utilized for analysis, akin to RECIST criteria. If there is geometric distortion, a region of interest will be placed in the undistorted region only. A histogram analysis method will be used to examine the distribution of ADC values within each region of interest (ROI). Only measurable disease defined as a primary tumor, a suspicious lesion, and/or an area of post-treatment change measuring at least 0.5 cm in two perpendicular dimensions will be used. Technically poor or non-diagnostic MR images will be excluded. ADCmean/min will be computed.

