## 7.0 STATISTICAL CONSIDERATION

### STATISTICAL ANALYSIS

Study Design and Endpoints: This is a pilot study designed as a paired, prospective, single-blinded study in which we compare the sensitivity and specificity of the optimized DWI sequence ADCmean/min versus FDG PET/CT SUVmax for the evaluation of recurrent SCC in post-treatment patients. The primary endpoints of sensitivity and specificity will evaluate the diagnostic accuracy of the optimized DWI sequence ADCmean/min versus the standard-of-care FDG PET/CT SUVmax. The secondary endpoint will evaluate if the enhanced DWI sequence can more expediently assess non-responders to treatment as compared to FDG PET/CT.

Aim 1: The 60 subject sample size for this pilot study was chosen for feasibility of recruitment based on the approximately 650 PET/CT exams performed for head and neck tumor in 2018. ROI will be used for statistical assessments of ADC measurements (see methodology of ADC measurement, above). FDG-PET SUVmax results will be used as the reference standard for tumor or non-tumor tissue. ADCmean, ADCmin and standard deviation will be used to describe distribution of ADC measurements (AADC) in tumor and non-tumor tissues and independent sample t-test will be used to compare ADC measurements between the two groups. Mean difference and 95% confidence interval around that will be used to interpret our results. For ROC analysis, the area under the curve (AUC) will be calculated and the Youden's J index will be used to identify the value of the predictor variable that optimized sensitivity and specificity. Youden's J index varies from 0-1. The threshold value that provides the value of the J index closer to 1 is the value with the best performance and discriminative power. PPV and NPV will also be evaluated. The logistic regression model allows for evaluating this impact after controlling for potential confounders. We will explore the linearity assumption of relationship of delta ADC with logit of outcome (response to treatment) and if the assumption is violated,

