polynomial effects will be explored, and data transformation will be employed as needed. All statistical analysis will be carried out by [name], a biostatistician in the ENT Department with extensive experience in head and neck cancer research. A 90% confidence interval will be calculated for the differences in sensitivity and specificity of the enhanced DWI sequence ADCmean/min as compared with the standard-of-care FDG PET/CT SUVmax. The positive and negative predictive values will also be evaluated. Since this is a pilot study, no existing data can be utilized to calculate a power analysis.

A binary logistic regression model will be utilized to evaluate the impact of the change in ADC in predicting early non-responders to treatment. A p-value will be calculated to evaluate if the enhanced DWI sequence can more expediently identify non-responders to treatment as compared to FDG PET/CT.

(\*\*Note: Patients who do not undergo SOC PET/CT at the 3-6 month time point will be considered inevaluable and will be replaced.)

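### The secondary model for early non-responders uses a change in ADC, but the plan schedules one DWI scan per patient and names no source for a second ADC

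*Combined protocol and SAP*

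**What the plan says.** The secondary endpoint in section 7.0 is whether DWI recognises treatment non-responders sooner than FDG PET/CT. One model is named for it: "A binary logistic regression model will be utilized to evaluate the impact of the change in ADC in predicting early non-responders to treatment". Aim 1 in the same section gives the predictor again under another name: "We will explore the linearity assumption of relationship of delta ADC with logit of outcome (response to treatment". The next sentence promises a p-value for DWI against PET/CT on speed of identification. It gives no test, null hypothesis, time variable or significance level.

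The imaging is described in two places. Section 1.0: "The patients will undergo an optimized research neck DWI protocol up to 3 weeks post-treatment". The Imaging Plan in section 4.0: "The patients will undergo an optimized research neck DWI MRI, up to 3 weeks post-treatment". Both go on to the standard-of-care PET/CT at 3-6 months, and section 2.0 states its hypothesis for the same post-treatment scan.

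Section 2.0 sets the gold standard as histology where it exists and/or clinical and imaging outcome at one year, and gives RECIST 1.1, PERCIST and iRECIST as examples of imaging measures.

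**The concern.** A change in ADC is a within-patient contrast between two time points, and the plan appears to measure only one. If so, the only model named for early non-responders has a predictor that the study does not collect. Identifying early non-responders is one of the two purposes given in section 1.0. If the gap is found only at analysis, someone must choose a substitute (ADCmean, ADCmin or an ad hoc baseline) with the data in view, and the result would be post hoc.

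The companion p-value adds a second gap. Without a named test or a PET term, it is unclear what comparison it would make. A comparison of timing alone would largely reflect the order of the visits.

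**Working it through.** The plan has no power calculation or other figure to reproduce here. The check sets the requirement beside what the plan supplies.

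**1. What the predictor needs.** For patient i, a change is ADC_i(time 2) − ADC_i(time 1), or a ratio of the two. Either needs at least 2 measurements per patient. The plan gives no change formula.

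**2. What the plan supplies.**

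| Source | Content | ADC time points |
|---|---|---|
| Sections 1.0, 2.0 and 4.0, text | One research DWI scan, up to 3 weeks post-treatment | 1 |
| Section 4.0, schedule table | DWI marked in 1 of 4 columns; not at baseline, 3-6 months or follow-up | 1 |
| Section 4.0, clinical data list | 26 items; one is "Date of Study MRI"; none is a baseline MRI date or baseline ADC | 1 |
| Section 4.0, ADC evaluation | "ADCmean/min will be computed" | 1 (two summaries of one scan) |

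Needed: 2. Described: 1. Patients with a computable change from the data described: 0 of 60.

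**3. Possible sources of a second ADC.**
- Section 1.0 calls the study longitudinal, and follow-up runs to one year. The follow-up consists of record review, with no second DWI.
- Record review is also planned at baseline. Nothing says that it yields an ADC, or that an earlier clinical MRI would use the research sequence.
- Eligibility reads "Must have had or be scheduled for standard-of-care surgical resection, radiation, and/or chemo-radiation". Patients already treated cannot have a pre-treatment research scan, and none is scheduled for those still awaiting treatment.
- Aim 1 contains the label AADC, possibly a garbled delta symbol. It is attached to ADC distributions in tumor and non-tumor tissue. A difference between groups cannot be a patient-level predictor.

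**4. The p-value.** The model as written is logit P(non-response) = b0 + b1 × (change in ADC) + confounders. A test of b1 asks whether ADC change is associated with outcome. With no PET term it cannot compare DWI with PET/CT. The data list includes "Length of time from MRI to clinical/radiographic progression", but nothing links that item to this p-value.

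Taking 3 and 6 months as about 13 and 26 weeks, the lead of DWI over PET/CT is:
- shortest: 13 − 3 = 10 weeks;
- longest: 26 − 0 = 26 weeks.

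DWI therefore comes first in every patient who keeps to the schedule.

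**5. The outcome.** The one-year window in section 2.0 contains the 3-6 month PET/CT, and PERCIST is a PET response criterion. PET can thus enter the reference against which PET is judged.

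**6. Precision of a paired comparison.** With discordant share d, n non-responders and no true difference, the 90% half-width is 1.645 × √(d/n). The documents give neither input, so these are assumptions:
- n = 20, d = 20%: 1.645 × √0.010 = 0.164;
- n = 10, d = 30%: 1.645 × √0.030 = 0.285.

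That is about ±16 to ±29 percentage points. It makes no allowance for choosing the DWI cut-off on the same data.

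**The case against.** The strongest reply has four parts.

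- **This is one secondary model in a pilot.** The 60 patients were chosen for feasibility, and the t-test, ROC analysis, sensitivity and specificity all run on the single ADC. This stands, and it limits the weight of the point. It does not supply the missing predictor.
- **A baseline ADC may be recorded elsewhere.** Section 4.0 refers to an attached data sheet that is not in the documents. A reader might infer that a change in ADC can never be obtained; the documents do not support that. They show only that no source for a second ADC is specified.
- **Non-response is not undefined.** A reader might infer that it is. In fact Aim 1 names treatment response as the model outcome, and section 2.0 lists a gold standard with response criteria. What remains is narrower: several criteria are offered, none is tied to this model, and some include PET.
- **The speed comparison need not mislead.** A reader might infer that the plan contains a timing test biased toward DWI. No timing test is proposed. Differences in sensitivity and specificity, with predictive values, are to be reported as well, so cases missed by DWI would be visible. What stands is that the p-value has no stated method.

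**Conclusion.** The contradiction is real. Section 7.0 twice names a change in ADC as predictor, and the rest of the plan describes one ADC time point. The secondary logistic model cannot be run from the data described, for any of the 60 patients. The accompanying p-value has no named test and cannot come from that model as a comparison with PET/CT.

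This should be fixed before analysis, but it is not a fundamental fault: it is confined to the secondary endpoint, and the trial's main accuracy analyses are unaffected by it. The conclusion assumes only that the schedule and data list mean what they say and that the unseen data sheet adds no baseline ADC. The lead time of about 10 to 26 weeks assumes adherence to both imaging windows.

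**What to change.** 1. In both places in section 7.0, replace the change in ADC with the single post-treatment ADC, using one metric (ADCmean or ADCmin) named before analysis. Alternatively, if a comparable baseline ADC exists for all patients, state its source and the change formula.
2. For this model, define non-response by the histology and/or 1-year outcome in section 2.0. Leave out the 3-6 month PET/CT and any PERCIST reading based on it, so that PET is not part of the reference it is compared with.
3. Drop the p-value on speed and report lead time descriptively.
4. Base the DWI-versus-PET comparison on the paired differences already planned in section 7.0 with 90% confidence intervals: sensitivity in non-responders, specificity in responders, both against the outcome in item 2. State that a Youden cut-off chosen on the same data makes DWI accuracy look optimistic.

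The cost is a text amendment, with no added scans. The claim about ADC change is lost unless a baseline source is documented. Fewer patients may have an outcome free of PET, and the intervals will be wide, as is usual in a pilot.

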## 2.0 OBJECTIVES

The Specific Aim of this application is as follows: To compare SUVmax and ADCmean/min values to assess the capability of the new DWI pulse sequence to differentiate post-treatment change from residual or early recurrent tumor.

Hypothesis: The optimized research DWI pulse sequence obtained up to 3 weeks post treatment will accurately identify residual/recurrent tumor, as confirmed by the clinical FDG PET/CT obtained at 3-6 months. This would potentially result in a modification of imaging follow-up algorithms, increased cost-savings and eliminate radiation exposure to patients inherent in PET/CT. This would also result in earlier changes to treatment regimens and stratify patients into more or less aggressive tumor response to treatment. The gold-standard will be histological tissue where available and/or 1-year clinical and imaging outcomes, including imaging outcome measurements such as RECIST 1.1 [De Bree, 2017], PERCIST [Joo Hyun, 2016] and iRECIST [Persigehl, 2020].

**Figure 1:** DWI data obtained from a healthy volunteer with a GE 3 Tesla system and eight-channel neurovascular array coil. Single-shot EPI-based DWI was obtained: matrix size = 128  $\times$  128; parallel imaging acceleration factor = 2; field of view = 24 cm  $\times$  24 cm; b-value = 1000 s/mm^2. B, High-resolution DWI data obtained with four-shot interleaved EPI pulse sequence (matrix size = 256  $\times$  256; field of view = 24 cm  $\times$  24 cm; b-value = 1000 s/mm^2) and reconstructed with our developed MUSE algorithm.

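### Replacing every patient without a 3-6 month PET/CT can drop early recurrences from the DWI accuracy analysis, although the Section 2.0 gold standard could classify them

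*Combined protocol and SAP*

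**What the plan says.** The rule stands as a note in Section 4.0 (Imaging Plan) and again at the end of Section 7.0: "Patients who do not undergo SOC PET/CT at the 3-6 month time point will be considered inevaluable and will be replaced". Neither place makes an exception by reason or defines inevaluable; its plain reading is that the patient is not analysed. The MRI is done up to 3 weeks after treatment, so months can pass before the PET window opens. Section 4.0 also says "Patients who sign the consent form but do not have the MRI will not be considered accrued on this study". A scanned patient who later misses the PET therefore does count as accrued.

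On what counts as truth, the document says two things. Section 2.0: "The gold-standard will be histological tissue where available and/or 1-year clinical and imaging outcomes". Section 7.0: "FDG-PET SUVmax results will be used as the reference standard for tumor or non-tumor tissue". The hypothesis in Section 2.0 also speaks of confirmation by PET/CT.

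Outcome data are collected whether or not a PET is done. Section 1.0: "We will follow patients for 1 year to assess their clinical outcomes, including histological results associated with re-biopsy or surgery". Section 4.0 adds that "medical records will be reviewed after scheduled SOC visits to additionally assess for clinical outcomes", and its data list includes biopsy, pathology-confirmed recurrence, date of recurrence and time from MRI to progression.

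The planned analyses include a comparison ("A 90% confidence interval will be calculated for the differences in sensitivity and specificity of the enhanced DWI sequence ADCmean/min", against PET), an ROC analysis in which the Youden "index will be used to identify the value of the predictor variable that optimized sensitivity and specificity", and positive and negative predictive values (PPV, NPV).

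**The concern.** The aim is to identify residual or early recurrent tumor from a very early scan. A recurrence established before 3 months, in a patient who then has no window PET, is exactly such a tumor. DWI either showed it or missed it, and the rule leaves it uncounted and fills the place with a patient who did reach the PET.

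If DWI-positive and DWI-negative tumor patients lose the PET at different rates, the primary endpoints are biased. If they lose it at the same rate, sensitivity is unbiased but rests on fewer tumors. If tumor patients lose it more often than tumor-free patients, prevalence falls in the analysed set and PPV and NPV shift.

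A link between MRI result and lost PET is plausible but not established. Section 4.0 (MRI Processing Guidelines) and Section 5.9 let urgent or incidental findings, including new tumor, reach the treating physician. They do not clearly cover low ADC at the treated site.

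**Working it through.** There is no plan figure to reproduce. The 60 is a feasibility number, and no power, recurrence rate or missing-PET rate is stated.

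**Which analyses need the PET?**

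| Analysis | Truth = Section 2.0 gold standard | Truth = PET SUVmax (Section 7.0) |
|---|---|---|
| Paired DWI-PET difference | PET needed | PET needed |
| DWI sensitivity, specificity, AUC, PPV, NPV | PET not needed | PET needed |

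The rule excludes too much only in the lower-left cell, and there the data to classify the patient are already planned.

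**Inputs.** From the documents: 60 analysed patients and the 90% confidence level. Assumed: tumor prevalence 30%, true DWI sensitivity S and specificity both 80%; a and b = PET loss in DWI-positive and DWI-negative tumor patients; c = loss in tumor-free patients, unrelated to ADC. DWI is scored against true tumor status.

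**Tumors excluded.** Tumor loss L = 0.8a + 0.2b. Per 60 scanned, pairs = 18(1−L) + 42(1−c). Scans for 60 pairs = 3600/pairs; tumors scanned = 0.30 × scans; tumors analysed = 60 × 18(1−L)/pairs.

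| a / b / c | L | Pairs per 60 | Scans | Tumors scanned | Tumors analysed |
|---|---|---|---|---|---|
| 20% / 5% / 0 | 0.17 | 56.94 | 63.2 | 19.0 | 15.7 |
| 40% / 10% / 0 | 0.34 | 53.88 | 66.8 | 20.0 | 13.2 |
| 40% / 10% / 10% | 0.34 | 49.68 | 72.5 | 21.7 | 14.3 |

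Varying prevalence in the second row: at 20%, pairs = 12 × 0.66 + 48 = 55.92, giving 64.4 scans, 12.9 tumors scanned and 8.5 analysed. At 40%, pairs = 24 × 0.66 + 36 = 51.84, giving 69.4 scans, 27.8 and 18.3.

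**Precision.** 90% half-width = 1.645 × √(0.16/n). With n = 20.0 it is 14.7 points; with n = 13.2 it is 18.1 points. This holds even if loss is unrelated to DWI.

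**Sensitivity at a fixed cutoff** = S(1−a) / [S(1−a) + (1−S)(1−b)], which does not depend on prevalence. For 40/10: 0.48/(0.48 + 0.18) = 72.7%.

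**Youden cutoff re-chosen in the retained patients.** Equal-variance binormal model with x = −ADC: tumor-free N(0,1), tumor N(1.683,1). The no-loss cutoff 0.842 gives 80/80. Tumor density is weighted by (1−a) above 0.842 and (1−b) below, and J is maximised.

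| a / b | Fixed-cutoff sensitivity | Re-chosen cutoff: sensitivity / specificity |
|---|---|---|
| 20 / 5 | 77.1% | 79.6 / 77.7% |
| 40 / 10 | 72.7% | 79.2 / 74.5% |
| 50 / 10 | 69.0% | 79.0 / 71.9% |
| equal | 80.0% | 80.0 / 80.0% |
| 5 / 20 | 82.6% | 82.6 / 80.0% |
| 10 / 40 | 85.7% | 85.7 / 80.0% |
| 10 / 50 | 87.8% | 87.8 / 80.0% |

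When DWI-positive tumors are the ones lost, re-choosing the cutoff moves most of the error to specificity. J is 0.60 with no loss, 0.54 at 40/10 and 0.66 at 10/40.

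**Predictive values when loss is unrelated to DWI** (34% of tumors lost, no tumor-free loss). Tumors kept: 18 × 0.66 = 11.88. Prevalence falls from 30.0% to 11.88/53.88 = 22.0%. PPV falls from 14.4/22.8 = 63.2% to 9.504/(9.504 + 8.4) = 53.1%. NPV rises from 33.6/37.2 = 90.3% to 33.6/(33.6 + 2.376) = 93.4%.

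**A check on the remedy.** Keeping patients merely because their status happens to be known creates the opposite problem. If 20% of tumor-free patients lack 1-year follow-up, prevalence rises to 18/(18 + 33.6) = 34.9%, PPV to 14.4/(14.4 + 6.72) = 68.2%, and NPV falls to 26.88/(26.88 + 3.6) = 88.2%. One ascertainment rule must apply to everyone.

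**The case against.** The strongest reply is that Section 7.0 contains no separate DWI analysis against histology or 1-year outcome. The endpoints compare DWI with PET, and the ROC work sits under PET SUVmax as the reference. Without a PET, the patient lacks either the comparator or the reference, so the rule is coherent on Section 7.0's own terms, and the real defect is the conflict with Section 2.0. This stands in part: if SUVmax is kept as the reference, the exclusion follows from it. But Section 2.0 states a gold standard that needs no PET, and against it the rule discards classifiable tumors.

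Second, the Section 2.0 gold standard goes on to mention PERCIST, a PET-based criterion, so patients without PET may lack an imaging component that others have. The wording there makes these criteria examples and joins histology and outcomes with and/or, so PET is not mandatory. The warning about unequal ascertainment is fair, and some patients may remain undetermined. They need to be counted, not dropped.

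Third, the rates have no anchor in the documents, and the Youden model makes PET loss jump at a cutoff that will be chosen only at analysis. Both points stand. The re-chosen-cutoff figures show where error can go and do not predict it. The mild case shifts sensitivity by 2.9 points, well inside a 90% half-width of 1.645 × √(0.16/15.74) = 16.6 points.

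**Conclusion.** The concern holds. The rule is unconditional and appears twice. Read with the Section 2.0 gold standard, it removes scanned patients whose tumor status can be established from planned data. What is certain is the rule; its effect is not. The number of tumors lost, and the size and direction of any bias in sensitivity and specificity, depend on PET-loss rates that the documents do not give. On the assumptions shown, the effect runs from negligible to several points in either direction. Precision is lost, and predictive values shift, even when PET loss has nothing to do with the DWI result, provided tumor patients miss the PET more often than tumor-free patients. If PET SUVmax is confirmed as the reference, the rule is coherent and what remains is a limit on whom the results apply to. The plan should be changed before analysis, since deciding afterwards who counts would be data-driven. The secondary analysis of change in ADC is outside this point.

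**What to change.** 1. Reconcile Sections 2.0 and 7.0 so that the Section 2.0 gold standard defines tumor status for DWI accuracy.
2. Replace the note in Sections 4.0 and 7.0 with wording such as:

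> All patients with an evaluable DWI MRI stay in the DWI accuracy analysis and are classified by the Section 2.0 gold standard, with the same ascertainment rule and follow-up to 1 year whether or not the 3-6 month PET/CT was done. Patients whose status remains undetermined are counted and reported. Patients without that PET/CT are left out only of the paired DWI-PET comparison and may be replaced to reach 60 pairs.

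3. Tabulate patients without a window PET by reason, DWI result and reference status, and state that the paired comparison applies only to patients who reached the PET.

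If PET SUVmax is kept as the reference, item 2 does not apply. Give the table and state that all accuracy results apply only to patients who reached the PET.

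The cost is an amendment to Sections 2.0, 4.0 and 7.0 and one table. Settling the reference standard is the larger part and is needed anyway. No scans are added: reaching 60 pairs takes about 67 MRIs at 40/10 (73 if 10% of tumor-free patients also miss PET) with or without the change, and the 1-year record review is already planned. The drawback is that the DWI accuracy and paired analyses will have different denominators, which must be shown.
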